#### 19. APPENDIX 1. PARTIAL DATE CONVENTIONS

As applicable, partial dates may be imputed for the purposes of categorizing medications as prior/concomitant and defining TEAs. Imputed dates will NOT be presented in listings. Conventions for imputing partial dates are described below. In general, partial date conventions are designed such that:

- If it is unclear whether or not a medication is prior or concomitant due to partial dates, the worst case will be assumed (i.e., concomitant).
- If it is unclear whether or not an AE is a TEAE due to partial dates, the worst case will be assumed (i.e., TEAE).

If a single medication or AE is reported more than once and partial date imputations cause the instances to appear overlapping, then the medication or AE will be assumed to be a single continuous instance. Start date will be assumed to be the earliest occurring started date (imputed or observed), and end date will be assumed to be the last occurring end date (imputed or observed).

**Table 1: Algorithm for Imputing Partial Dates** 

Missing data element				Imputation rule
Start date or stope date?	Day	Month	Year	
Start Date	Yes	No	No	If the non-missing month is the same as the month of study medication start, impute study medication start date.  Otherwise, impute the first day of the non-missing month.
Start Date	Yes	Yes	No	If the non-missing year is the same as the year of study medication start, impute study medication start date.  Otherwise, impute the first day of the non-missing year (i.e., January 1 st ).

Document: Statistical Analysis Plan: AEGR-734-401: A 36-Month, Multicenter, Open Label Phase 4 Study to Evaluate the

Immunogenicity of Daily SC Metreleptin Treatment in Patients with Generalized Lipodystrophy

Author: [name], [name], [name], [name] Version Number: 2.1

Version Date: 13MAR2024

Copyright © 2018 IQVIA. All rights reserved. The contents of this document are confidential and proprietary to IQVIA Holdings Inc. and its subsidiaries. Unauthorized use, disclosure or reproduction is strictly prohibited.

Start Date	Yes	Yes	Yes	Impute study medication start date.
Stop Date	Yes	No	No	If study discontinuation date occurred during the non-missing month, impute study discontinuation date.
				Otherwise, impute the last day of the non-missing month.
				If study discontinuation date occurred during the non-missing year, impute study discontinuation date.
Stop Date	Yes	Yes	No	
				Otherwise, impute the last day of the non-missing year (i.e.,
				December 31 st ).
Stop Date	Yes	Yes	Yes	Impute study discontinuation date.

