8.3 Recording of Adverse Events

8.3.1 Time Period for Collection of Adverse Events

Adverse events (AE), including serious adverse events (SAE), AEs leading to discontinuation and AESIs will be recorded from the signing of the informed consent or if the AE or AESI is related to study procedure.

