#### 13. MEDICATIONS

Medications will be presented for the SAF and coded using the latest version of the World Health Organization Drug Dictionary (WHO-DD) at database lock. Medications will be categorized as prior or concomitant, and the total number of patients in each category will be summarized by anatomic therapeutic class level 3 and preferred name.

If it is unclear whether or not a medication is prior or concomitant due to partial dates, the worst case will be assumed (i.e., concomitant). See **Appendix 1** for handling of partial dates.

- 'Prior' medications are medications which the patient started and stopped prior to the first dose of study medication.
- 'Concomitant' medications are medications which:
  - O Started prior to, on or after the first dose of study medication and started no later than 14 days following end of study medication,
  - AND ended on or after the date of first dose of study medication or were ongoing at the end of the study.

See **Section 8.1** Statistical Summaries, Tests and Confidence Intervals for a description of statistics to be reported.

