#### 17.1 Adverse Events

Adverse Events (AEs) will be coded using the latest version of MedDRA, and summarized by SOC, preferred name, and intensity. Intensity is captured in the CRF. See **Section 8.1** Statistical Tests and Confidence Intervals for a description of summaries to be reported.

Adverse Events of Special Interest (AESIs) are defined as:

- The presence of Category D or E *in vitro* cell-based NAb activity (or the relevant corresponding test result from the ligand-binding method) to metreleptin
- Necrotizing pancreatitis
- Hepatic adverse events including potential drug induced liver injury (DILI)
- Severe hypoglycemia
- Severe hypersensitivity reactions
- New diagnoses of autoimmune disorders (for instance, autoimmune hepatitis, glomerulonephritis, lupus erythematosus, antiphospholipid antibody syndrome, rheumatoid arthritis)
- Autoimmune disease exacerbation
- Serious infection resulting in hospitalization
- All cancers (excluding non-melanoma skin cancer) by cancer type
- Exposed pregnancies and pregnancy outcomes.

TEAEs are defined as AEs that started or worsened in severity on or after the first dose of study medication. If it is unclear whether or not an AE is a TEAE due to partial dates, the worst case will be assumed (i.e., TEAE). See **Appendix 1** for handling of partial dates.

AEs, serious AEs (SAEs), AEs of special interest (AESIs), TEAEs, AEs possibly caused by metreleptin, and AEs leading to metreleptin discontinuation will be summarized by ADA positivity and titer, cell-based NAb positivity and titer, and RB positivity, titer, and quintile of percent

Document: Statistical Analysis Plan: AEGR-734-401: A 36-Month, Multicenter, Open Label Phase 4 Study to Evaluate the

Immunogenicity of Daily SC Metreleptin Treatment in Patients with Generalized Lipodystrophy

Author: [name], [name], [name], [name] Version Number: 2.1

inhibition. For each patient, only one event of each type will be selected to include in summary outputs. If a patient has multiple events the same type, the event with the highest severity level is selected. For patients with multiple events of the same type and severity, the event corresponding to the highest titer or percent inhibition level is selected. The corresponding titer and percent inhibition level are defined by the most recent measurement occurring prior to the event start date.

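### SAP Appendix 1 moves partial start dates to the first dose without checking the stop date, so an event known to have ended before dosing becomes a TEAE and a medication stopped before dosing falls in no category

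*SAP*

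**What the plan says.** SAP Appendix 1, Table 1 has three start-date rows that can lead to the first-dose date:

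- Day missing: "If the non-missing month is the same as the month of study medication start, impute study medication start date".
- Day and month missing: "If the non-missing year is the same as the year of study medication start, impute study medication start date".
- Everything missing: always "impute study medication start date".

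No row mentions the stop date, and the Appendix has no check that an imputed start comes before a known stop.

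Three definitions use the result:

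- SAP Section 17.1: "TEAEs are defined as AEs that started or worsened in severity on or after the first dose of study medication". The stop date plays no part.
- SAP Section 13 defines prior medications as "medications which the patient started and stopped prior to the first dose of study medication".
- SAP Section 13 sets two conditions for concomitant medications. The second is "AND ended on or after the date of first dose of study medication or were ongoing at the end of the study".

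The text introducing Table 1 gives the principle behind it: "If it is unclear whether or not an AE is a TEAE due to partial dates, the worst case will be assumed (i.e., TEAE". A parallel sentence makes concomitant the default for medications of unclear status.

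Pre-dose adverse events are in scope. Protocol Section 8.3.1 says that they "will be recorded from the signing of the informed consent", and Protocol Table 1 allows screening from 28 days before the first dose.

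**The concern.** A record whose stop date is known to precede the first dose has only one possible status. The event or drug must have started before dosing, so the event is not treatment-emergent and the drug is prior. Table 1 still gives it a start on the day of first dose.

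TEAE status carries more weight since the 16Dec2024 change to the SAP, which restricts the adverse event tables by antibody and neutralizing status to TEAEs. Those tables address the safety objective, and a pre-dose event cannot be a consequence of antibodies to metreleptin. For medications, the rule can drop a drug from both halves of the prior/concomitant table. Imputed dates are kept out of the listings (SAP Section 8.2 and Appendix 1), so the impossible order of dates would not be visible there.

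**Working it through.** The documents give no figure for this rule, so there is nothing to reproduce. The check applies the rules literally.

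**Rules.** Let F be the first-dose date, S the start date after imputation and E the stop date.

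- Table 1: S = F if the start is known only to the month and that is the dosing month, or only to the year and that is the dosing year, or not at all.
- TEAE (Section 17.1): S ≥ F. Worsening after F is impossible once the event has ended before F.
- Prior (Section 13): S < F and E < F.
- Concomitant (Section 13): S no later than 14 days after the end of study medication, and E ≥ F or ongoing.

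**Logic.** If S is set to F and E < F, then S > E. The TEAE condition is met because S = F. Prior fails because S is not before F. Concomitant fails because E is before F.

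**Worked cases**, with F = 20 Jun 2020 (illustrative dates):

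| Known part of start | Stop | Imputed start | As an AE | As a medication |
|---|---|---|---|---|
| Jun 2020 | 10 Jun 2020 | 20 Jun 2020 | TEAE | no category |
| 2020 | 10 Mar 2020 | 20 Jun 2020 | TEAE | no category |
| nothing | 10 Mar 2018 | 20 Jun 2020 | TEAE | no category |
| May 2020 (control) | 10 Jun 2020 | 1 May 2020 | not TEAE | prior |
| Jun 2020 (control) | 25 Jun 2020 | 20 Jun 2020 | TEAE | concomitant |
| 5 Jun 2020, complete (control) | 10 Jun 2020 | none needed | not TEAE | prior |

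The three cases with a partial or missing start and a pre-dose stop fail. The controls are classified correctly.

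**All same-month combinations.** Take every first-dose day in a 365-day year and every complete stop date earlier in the same month, with only the start day missing. A month of n days gives n(n − 1)/2 pairs, so the total is 7 × 465 + 4 × 435 + 378 = 5373. All 5373 give a TEAE, and all 5373 give a medication in no category. This confirms the logic; it says nothing about frequency.

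**Limit of scope.** A stop date with the day missing in the dosing month is imputed to the end of that month, or to the study discontinuation date if that falls in it. The stop then falls on or after F and the worst case applies, as intended. The defect needs a stop date known to precede F.

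**Size.** SAP Section 4.1 gives 11 patients, and 1/11 = 9.1%. Section 17.1 takes one event of each type per patient, so a misfiled event adds a patient to a row only if that patient has no other TEAE there. About 9 points is therefore a maximum for one misfiled event with all 11 patients as denominator.

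**With a stop-date rule added** (E < F makes the event not a TEAE and the medication prior), all three failing cases are classified correctly and the controls do not change.

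**The case against.** The strongest defence is that Table 1 does not stand alone. SAP Section 8.2 and Appendix 1 permit imputation rather than require it, only where applicable, and the conventions are meant for unclear cases. A careful programmer could conclude that a known pre-dose stop settles the matter and skip imputation. That is true, but it requires departing from the table, and nothing in the text says to do so. For medications the literal result is not even the stated default of concomitant.

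The practical reach may also be small. The pre-dose period is short, missing data are queried (Protocol Sections 11.4 and 12.9), the study is descriptive, and the prior-medication table feeds no primary, secondary or safety outcome. At Screening, Protocol Section 6.2.1 has prior drugs reviewed, but names only concomitant lipid-lowering and antidiabetic use for recording in the eCRF. How many already-stopped drugs reach the database is therefore unknown. These points stand and limit the weight of the finding. SAP Section 13 does plan a prior category, so such records are expected.

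A reader might infer three stronger things that the documents do not support:

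- That misfiled events are tied to the Day 0 antibody sample. Section 17.1 requires a measurement before the event start date. The imputed start is the date of the baseline sample, and Protocol Table 1 schedules no antibody sample at Screening. Read literally, the event links to no scheduled measurement.
- That the first row would match the same month in a different year. That row applies only when the year is known, and its alternative, the first of the month, makes sense only for a month in a given year. Adding the year would only clarify the wording.
- That results are in fact 9 points out. No affected record has been identified.

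**Conclusion.** The rule is wrong as written; this is not a case of missing detail. In three defined situations Table 1 gives an impossible date order, turns an event that ended before dosing into a TEAE, and leaves a drug stopped before dosing without a category. This goes against the principle stated in the same Appendix.

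The number of affected records cannot be derived from the documents. It is probably small for adverse events; incomplete start dates are more plausible for medications, which is an assumption. The maximum of about 9 points assumes one misfiled event, all 11 patients in the denominator and no other TEAE for that patient in the row. A smaller denominator n would make the step 1/n, and the documents give no stratum sizes.

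The visible change-record entries do not touch Appendix 1. Parts of that record were not available, so a later correction cannot be excluded.

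**What to change.** Add to SAP Appendix 1 a classification rule that takes precedence over Table 1:

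> If the complete or partial stop date shows that the AE or medication ended before the first dose of study medication, the start date is not imputed to the first-dose date; the AE is not a TEAE and the medication is prior. No imputed start date may be later than the known stop date.

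The rule classifies directly and does not prescribe a replacement start date, so it also works when the start date is wholly missing.

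The change record of 26Feb2025 shows that database lock has passed. The practical step is to search the analysis data for imputed starts later than known stops, correct the TEAE flag or medication category where any are found, and document the correction. If there are none, a one-line statement to that effect closes the point. Specifying both month and year in the first row is optional.

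The cost is a two-sentence rule in the SAP or its change record, one condition in the program and one data check. No new data are needed.

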#### 20. APPENDIX 2. WINDOWING CONVENTIONS

The below windowing conventions will be used to categorize all study assessments, including assessments occurring during unscheduled visits, into time periods of interest. Days are counted from the date of baseline visit where Baseline is defined as Day 0.

Only one assessment of each type will be presented from each analysis window. If more than one assessment of the same type occurs within an analysis window, then the maximum severity result will be selected for presentation. If more than one assessment of each types occurs within the maximum severity category, the result closest to the end of the analysis window will be selected. If the concept does not apply, then the result closest to the end of the analysis window will be selected.

The result closest to the end of the analysis window is preferred since the end of the analysis window aligns with the end of the visit window in all cases while the beginning of the analysis window may precede the beginning of the visit window. Therefore, the result closest to the end of the analysis window is most likely to be within the visit window.

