7.3 Immunogenicity

7.3.1 Collection of Samples for Measurement of Antibodies to Metreleptin and Leptin and *In Vitro* Neutralizing Activity

Blood samples for the measurement of antibodies to metreleptin and human leptin will be collected at the times specified in the Study Plan (Table 1). A cell-based assay and a receptor-binding assay will be used to measure *in vitro* neutralizing activity in all samples that test positive for antibodies to metreleptin and/or leptin (titer ≥ 5). The study lab manual will provide specific instructions for collection, processing, packaging, and shipping of all samples.

Additional safety samples for measurement of antibodies to metreleptin and human leptin will be collected if clinically indicated (e.g., loss of response to MYALEPT, or if patient develops a severe infection and/or sepsis), or at the discretion of the Investigator. The date, time of collection, and results (values, units, and reference ranges) will be recorded on the appropriate eCRF.

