8.3.8 Adverse Events of Special Interest

Adverse events of special interest will be collected and recorded in the eCRF.

A sample should be collected for measurement of *in vitro* neutralizing activity in all patients with the following AEs of special interest: suspected loss of response (worsening of metabolic control) or suspected loss of endogenous leptin action (severe infections or sepsis).

For patients who become pregnant during the study, a sample should also be collected to measure *in vitro* neutralizing activity at the time the pregnancy is identified. The patient

Confidential Page 40 of 58

will be allowed to continue in the study; however, the decision as to whether to continue metreleptin therapy during the pregnancy will be at the discretion of the treating physician. The pregnancy and all pregnancy outcomes should be reported as an AESI and followed by the patients' prescribing physician.

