10.5 Methods for Statistical Analyses

There will be no hypothesis testing. All data will be summarized by descriptive statistics and/or listings. In general, continuous variables will be summarized by n, mean, SD, median, min and max. Number of patients and percentage of patients in a category will be provided.

Descriptive statistics will be provided for immunogenicity variables (Section 10.4). The maximum antibody titer (anti-metreleptin or anti-HuL) during a visit will be summarized by visit. Categorization of *in vitro* neutralizing activity as assessed by cell-based assay will be summarized across visits; the rate of Category D and E *in vitro* neutralizing activity with 90% and 80% exact confidence intervals will be computed. The results are reported as percent inhibition and 80% inhibition is currently utilized as the neutralizing antibody threshold. activity Results for *in vitro* neutralizing activity will be summarized across visits; however, there will be no formal comparison of the 2 assay methods for the detection and relative potency of Category D or E *in vitro* neutralizing activity.

Maximum antibody titers, neutralizing activities detected by both methods, and metreleptin exposure for each patient will be plotted over time. Maximum antibody

Confidential Page 47 of 58

titers, neutralizing activities detected by both methods, and any associated clinical events (i.e., loss of efficacy or AE) will be summarized.

All AEs will be coded using the Medical Dictionary for Regulatory Activities (MedDRA). The number and percentage of patients who experienced at least 1 AE will be summarized by system organ class and preferred term. AEs will be summarized by relationship to the study medication and by severity. Deaths, SAEs, AESIs, and AEs leading to discontinuation will be tabulated and/or listed. SAEs, AESIs and AEs leading to discontinuation will be summarized respectively by peak antibody titers (antimetreleptin, anti-HuL) and by *in vitro* neutralizing activity categories or percent inhibition.

Clinical laboratory results (hematology, chemistry, and urinalysis), and vital signs results will be summarized using descriptive statistics for each visit.

Change from baseline in HbA1c and percent change from baseline in fasting triglycerides will be summarized for each visit by overall patient population, by peak antibody titers (anti-metreleptin, anti HuL), and by *in vitro* neutralizing activity categories or percent inhibition , respectively.

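### Event-triggered antibody samples can displace the scheduled sample in the primary by-visit tables, because SAP Appendix 2 pools both and keeps the most severe or the latest result

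*SAP*

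**What the plan says.** SAP Appendix 2 applies its windows to all study assessments, "including assessments occurring during unscheduled visits". Where a window holds several results of one type, only one is presented: "If more than one assessment of the same type occurs within an analysis window, then the maximum severity result will be selected for presentation". For results to which severity does not apply, there is a fallback: "If the concept does not apply, then the result closest to the end of the analysis window will be selected".

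The change record dated 16 December 2024 ties data from a CRF-defined visit to that visit and extends each window on both sides. In the text available it does not say which result is kept when a scheduled and an unscheduled sample fall in the same window.

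On sampling, Protocol 7.3.1 says: "Additional safety samples for measurement of antibodies to metreleptin and human leptin will be collected if clinically indicated". It gives loss of response and severe infection or sepsis as examples, and also allows extra draws at the investigator's discretion. Protocol 8.3.8 asks for a neutralizing-activity sample when loss of response or loss of endogenous leptin action is suspected, and when a pregnancy is identified.

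On reporting, Protocol 10.5 states: "The maximum antibody titer (anti-metreleptin or anti-HuL) during a visit will be summarized by visit". SAP 15.2 reports binding-antibody (ADA), cell-based neutralizing (NAb) and receptor-blocking (RB) results by study visit, with 90% and 80% exact intervals on the positivity rates. SAP 4.3 declares no change from the protocol's analysis.

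**The concern.** The by-visit tables are meant to show how antibodies develop over time (Protocol 2.2). Protocol 2.1 explains that this time course is poorly defined in lipodystrophy because earlier sampling was inconsistent between patients. The fixed visit schedule is the remedy for that, and Appendix 2 lets uneven sampling back in.

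The extra draws are not random. They go mainly to patients showing the suspected consequences of neutralizing antibodies. Such a patient may contribute the worst of several draws to a visit, while a patient without events contributes one. Baseline is Day 0 only, so it is normally a single draw against which later worst-in-window results are read. The protocol's maximum is taken within a visit; the SAP's is taken across a window of weeks to months.

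What is at stake is the meaning of the primary by-visit rates and their intervals. A reader will take them as the proportion positive at about Month 12 or Month 18. They may instead partly reflect who was sampled more often, and why.

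**Working it through.** **1. The plan's own interval.** Protocol 10.2 gives 0.00 (0.00, 0.26) as the 90% interval for 0 of 10. The exact upper limit is 1 - 0.05^(1/10) = 0.2589, so the figure is reproduced. With the SAP's 11 patients (SAP 4.1), all assumed to have a result at the visit:
- 0/11: upper limit 1 - 0.05^(1/11) = 0.238, so 0-24%.
- 1/11 = 9%: Clopper-Pearson 0.005 to 0.364, so 0.5-36%.

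One triggered positive replacing one scheduled negative makes that difference.

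**2. Window lengths** (updated table in the change record; last day - first day + 1):

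| Month | Analysis window (days) | Length |
|---|---|---|
| 1 | 1-44 | 44 |
| 2 | 45-90 | 46 |
| 4 | 91-151 | 61 |
| 6 | 152-227 | 76 |
| 9 | 228-314 | 87 |
| 12 | 315-455 | 141 |
| 18 | 456-637 | 182 |
| 24 | 638-820 | 183 |
| 30 | 821-1002 | 182 |
| 36 | 1003 onward | open-ended |

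The visit windows themselves are 15 days (±7) up to Month 9 and 29 days (±14) from Month 12.

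**3. Effect of the number of draws under the maximum rule.** Let p be the chance that one sample is positive and k the number of samples in the window. If draws are independent, P(any positive) = 1 - (1 - p)^k. For correlated draws I use a latent-normal model with common correlation r and cut-off t = Φ⁻¹(1 - p):

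P(any positive) = 1 - ∫ Φ((t - √r·x)/√(1 - r))^k φ(x) dx.

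The documents give neither k nor r. With p = 0.10 assumed:

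| Draws | Independent | r = 0.5 | r = 0.8 | r = 0.95 |
|---|---|---|---|---|
| 1 | 0.10 | 0.10 | 0.10 | 0.10 |
| 2 | 0.19 | 0.17 | 0.14 | 0.12 |
| 3 | 0.27 | 0.22 | 0.17 | 0.13 |

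**4. Effect of why the sample is drawn.** Suppose a fraction f of patients has a triggered sample in a window, positive with probability q independently of the scheduled result. The by-visit rate is then p + (1 - p)·f·q. With p = 0.10 and f = 0.20 (both assumed), q = 0.1, 0.3 and 0.5 give 0.118, 0.154 and 0.190. With one scheduled sample per patient per window, the rate is p whatever the extra sampling.

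**5. The fallback.** If severity is held not to apply to titers or categories, the result nearest the window's end is kept. The push from frequency alone then goes, but displacement remains. At Month 12 the visit window ends on Day 378 and the updated analysis window on Day 455, so a triggered sample drawn after the scheduled one and up to Day 455 replaces it. Appendix 2 justifies the fallback by saying the two window ends always coincide. That does not hold for any post-baseline window in the updated table.

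**The case against.** The other side has several good points.

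- **Events and antibody status.** A reader might infer that the rule itself ties positivity to having an event in the safety tables. It does not. SAP 17.1 classifies an event by the most recent measurement before its start date. A sample triggered by an event follows its onset and cannot classify that event, though it could classify a later one. This stands in full, and the concern is confined to the by-visit tables.
- **The maximum is the protocol's choice.** Protocol 10.4 and 10.5 already call for the maximum titer by visit, and a worst-in-window rate is a legitimate period measure. The patient added in the 1/11 example did test positive in that period. This stands, but stretching the maximum from a visit to a window is new, and the tables are labelled by visit.
- **Severity is undefined** for titers, categories and laboratory values, so the maximum rule may not apply to them. This stands as an ambiguity. The protocol's maximum-titer wording favours the maximum reading for titers, and the fallback still permits displacement. A systematic worsening of laboratory means cannot be asserted.
- **Results within a patient should agree closely.** Protocol 2.1 describes antibodies that plateau and rarely disappear, and SAP 15.2 puts an unconfirmed cell-based detection in Category B, which is not positive. Independence is therefore the upper case, and the high-correlation columns are more plausible.
- **Growth over time.** A reader might infer that inflation increases with later visits because windows lengthen. That needs a constant rate of extra draws, which the documents do not give. With an assumed 2 independent extra draws per patient-year and a flat true rate of 0.10, the rate is 1 - 0.9·exp(-0.2·L/365.25): 0.121 for L = 44 (Month 1) and about 0.185 for L = 182 (Month 18). Month 36 counted to Day 1108 has L = 106 and gives 0.151, so even then the pattern is not a steady rise.
- **Stakes.** There is no hypothesis testing, and Protocol 10.2 says the study is not designed to estimate the neutralizing rate precisely. That limits the consequence but does not make the tables easier to read.

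**Conclusion.** The point holds for the primary by-visit ADA, NAb and RB tables. A triggered sample can displace the scheduled one under either branch of the selection rule. Under the maximum branch the direction is certain: rates stay the same or rise with sampling intensity. Under the fallback the direction is open.

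The size cannot be fixed from the documents. If no extra samples were drawn, or if results within a window always agree, nothing changes. For an assumed 10% per-sample rate, two or three draws raise it to somewhere between 12-13% (correlation 0.95) and 19-27% (independent). With about 11 patients, a single replaced result is visible in the table.

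The ever-positive and peak measures also depend on how often a patient is sampled. That follows from their definition and is not caused by Appendix 2.

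Part of the change record is not in the text available, including most of the entries made after database lock. A later change to the selection rule cannot be excluded, and the conclusion is conditional on there being none.

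**What to change.** In Appendix 2, base every by-visit immunogenicity table on the scheduled (CRF-visit) sample. Use an unscheduled sample from the same window only where the scheduled one is missing. Show unscheduled results in listings and in patient profiles.

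Keep all samples in the main ever-positive and peak measures. Restricting these to scheduled samples could drop a triggered Category D or E result from the headline, and such a result is itself an adverse event of special interest (Protocol 8.2). A scheduled-only version can be added as an optional sensitivity column.

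Because the database is locked, record the rule in the change file and report the tables as a documented additional analysis.

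The cost is one selection rule and a rerun of the by-visit tables, with no new data. The small downside is that a worst value between visits appears in the listings and in the ever-positive and peak measures rather than in the by-visit table.
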